7.0 Adverse Events List and Reporting Requirements

THE USE OF LIPOSOMAL BUPIVACAINE FOR PAIN CONTROL FOLLOWING MASTECTOMY AND IMMEDIATE IMPLANT BASED BREAST RECONSTRUCTION

Wake Forest Baptist Comprehensive Cancer Center
CCCFU # 99517

7.1 Adverse Event List for Liposomal Bupivacaine:

Common adverse reactions (incidence 2-10%): pyrexia, dizziness, peripheral edema, anemia, hypotension, pruritis, tachycardia, headache, insomnia, anemia postoperative, muscle spasm, hemorrhagic anemia, back pain, somnolence, procedural pain.²⁸

Rare adverse reactions (incidence <2%): chills, erythema, bradycardia, anxiety, urinary retention, pain, edema, tremor, dizziness postural, paresthesia, syncope, incision site edema, procedural hypertension, procedural hypotension, procedural nausea, muscular weakness, neck pain, pruritus generalized, rash pruritic, hyperhidrosis, cold sweat, urticaria, bradycardia, palpitations, sinus bradycardia, supraventricular extrasystoles, ventricular extrasystoles, ventricular tachycardia, hypertension, pallor, anxiety, confusional state, depression, agitation, restlessness, hypoxia, laryngospasm, apnea, respiratory depression, respiratory failure, body temperature increased, blood pressure increased, blood pressure decreased, oxygen saturation decreased, urinary incontinence, vision blurred, tinnitus, drug hypersensitivity, and hypersensitivity.²⁸

None of these adverse effects are expected to occur as a result of the administration of liposomal bupivacaine.

7.2 Adverse Event List for Bupivacaine:

The major cause of adverse reactions is secondary to high plasma levels of the medication. In this setting, CNS reactions include restlessness, anxiety, dizziness, tinnitus, blurred vision, tremors, drowsiness, unconsciousness. High doses can depress the myocardium leading to decreased cardiac output, heart block, hypotension, bradycardia, arrhythmias, cardiac arrest. Allergic reactions are rare but can include urticaria, pruritus, erythema, angioneurotic edema, tachycardia, nausea, vomiting, anaphylactoid-like symptoms³¹.

None of these adverse effects are expected to occur as a result of the administration of liposomal bupivacaine.

7.3 Adverse Event Characteristics

- **CTCAE term (AE description) and grade:** The descriptions and grading scales found in the revised NCI Common Terminology Criteria for Adverse Events (CTCAE) version 4.0 will be utilized for AE reporting. All appropriate treatment areas should have access to a copy of the CTCAE version 4.0. A copy of the CTCAE version 4.0 can be downloaded from the CTEP web site (<http://ctep.cancer.gov>).
- **‘Expectedness’:** AEs can be ‘Unexpected’ or ‘Expected’ (see Section 7.1 above) for expedited reporting purposes only.
- **Attribution** of the AE:
 - Definite – The AE is **clearly related** to the study treatment.
 - Probable – The AE is **likely related** to the study treatment.
 - Possible – The AE **may be related** to the study treatment.
 - Unlikely – The AE is **doubtfully related** to the study treatment.
 - Unrelated – The AE is **clearly NOT related** to the study treatment.

**THE USE OF LIPOSOMAL BUPIVACAINE FOR PAIN CONTROL FOLLOWING
MASTECTOMY AND IMMEDIATE IMPLANT BASED BREAST RECONSTRUCTION**
Wake Forest Baptist Comprehensive Cancer Center
CCCWU # 99517

7.4 STRC SAE Reporting Requirements

The Safety and Toxicity Reporting Committee (STRC) is responsible for reviewing SAEs for WFBCCC Institutional studies as outlined in Appendix B. STRC currently requires that all unexpected 4 and all grade 5 SAEs on these trials be reported to them for review. All WFBCCC Clinical Research Management (CRM) staff members assisting a Principal Investigator in investigating, documenting and reporting an SAE qualifying for STRC reporting are responsible for informing a clinical member of the STRC as well as the entire committee via the email notification procedure of the occurrence of an SAE. All adverse events will be recorded and the data will be managed in WISER. As such, the STRC will have access to all adverse events in the course of the study.

7.5 WFUHS IRB AE Reporting Requirements

Any unanticipated problems involving risks to subjects or others and adverse events shall be promptly reported to the IRB, according to institutional policy. Reporting to the IRB is required regardless of the funding source, study sponsor, or whether the event involves an investigational or marketed drug, biologic or device. Reportable events are not limited to physical injury, but include psychological, economic and social harm. Reportable events may arise as a result of drugs, biological agents, devices, procedures or other interventions, or as a result of questionnaires, surveys, observations or other interactions with research subjects.

All members of the research team are responsible for the appropriate reporting to the IRB and other applicable parties of unanticipated problems involving risk to subjects or others. The Principal Investigator, however, is ultimately responsible for ensuring the prompt reporting of unanticipated problems involving risk to subjects or others to the IRB. The Principal Investigator is also responsible for ensuring that all reported unanticipated risks to subjects and others which they receive are reviewed to determine whether the report represents a change in the risks and/or benefits to study participants, and whether any changes in the informed consent, protocol or other study-related documents are required.

Any unanticipated problems involving risks to subjects or others occurring at a site where the study has been approved by the WFUHS IRB (internal events) must be reported to the WFUHS IRB within 7 calendar days of the investigator or other members of the study team becoming aware of the event.

Any unanticipated problems involving risks to subjects or others occurring at another site conducting the same study that has been approved by the WFUHS IRB (external events) must be reported to the WFUHS IRB within 7 calendar days of the investigator or other members of the study team becoming aware of the event.

Any event, incident, experience, or outcome that alters the risk versus potential benefit of the research and as a result warrants a substantive change in the research protocol or informed consent process/document in order to insure the safety, rights or welfare of research subjects.

8.0 Pharmaceutical Information

**THE USE OF LIPOSOMAL BUPIVACAINE FOR PAIN CONTROL FOLLOWING
MASTECTOMY AND IMMEDIATE IMPLANT BASED BREAST RECONSTRUCTION**
Wake Forest Baptist Comprehensive Cancer Center
CCCWU # 99517

A list of the adverse events and potential risks associated with the commercial agents administered in this study can be found in Section 7.1 and 7.2.

8.1 Pharmaceutical Accountability

Drug accountability logs will be maintained for all agents used under this protocol. These logs shall record quantities of study drug received and quantities dispensed to patients, including lot number, date dispensed, patient identifier number, patient initials, protocol number, dose, quantity returned, balance remaining, and the initials of the person dispensing the medication.

8.2 Liposomal Bupivacaine

Product description: 20 ml liposomal bupivacaine (266 mg)

Solution preparation: Will be diluted in 10 ml of 0.25% Bupivacaine and 30 ml of 0.9% NaCl for a total solution volume of 60 ml per patient (30 ml per breast)

Storage requirements: Vials of Exparel should be inverted multiple times to re-suspend the particles immediately prior to withdraw from the vial.

Stability: Diluted suspensions should be used within 4 hours of the preparation.

Route of administration: Injection into surgical site including mastectomy skin flaps and wound bed after mastectomy and before breast reconstruction.

Disposal: There should be no additional product to dispose after injection

8.3 Bupivacaine

Product description: 60 ml of 0.25% bupivacaine

Solution preparation: No further dilution is required. 30 ml of 0.25% bupivacaine will be delivered to each breast.

Storage requirements: Can be stored at room temperature. The pharmacy will store and create the syringes including the medications to be administered.

Stability: The dosage of the above bupivacaine is stable and will not change over time

Route of administration: Injection into surgical site including mastectomy skin flaps and wound bed after mastectomy and before breast reconstruction.

Disposal: There should be no additional product to dispose after injection

THE USE OF LIPOSOMAL BUPIVACAINE FOR PAIN CONTROL FOLLOWING
MASTECTOMY AND IMMEDIATE IMPLANT BASED BREAST RECONSTRUCTION

Wake Forest Baptist Comprehensive Cancer Center
CCCWFU # 99517

9.0 Data Management

Informed consent document	EPIC
Protocol registration form	WISER/OnCore
Life Orientation Test-Revised	REDCap
PROMIS- Depression	REDCap
PROMIS- Anxiety	REDCap
Pain Catastrophizing Scale	REDCap
Visual analog scores	REDCap
Daily Pain Diary and Pain Rating	REDCap
Weekly Disability Assessment	REDCap
Adverse Effects	WISER

THE USE OF LIPOSOMAL BUPIVACAINE FOR PAIN CONTROL FOLLOWING
MASTECTOMY AND IMMEDIATE IMPLANT BASED BREAST RECONSTRUCTION

Wake Forest Baptist Comprehensive Cancer Center
CCCWU # 99517

10.0 Statistical Considerations

10.1 Analysis of Primary Objective

10.1.1 The study will allow for an attrition rate of 10%. Assuming a similar standard deviation in pain score at 48 hours for the local infiltration of liposomal bupivacaine and bupivacaine arms, with a 2-sided alpha of 0.05 and power of 80%, the study would have the ability to detect an effect size (absolute value of difference in sample means divided by the standard deviation) of 0.6 between the 2 groups with 25 subjects per arm. We will recruit 25 subjects per arm; if there is no attrition, with the same alpha and power as above, the study would have the ability to detect an effect size of 0.57. The primary outcome will be the pain score observed at 48 hours. To test for differences in these scores between the 2 arms, an independent t-test will be used; if the observed p-value is <0.05, statistical significance will be assumed. Two-sided ANOVA will be performed for statistical analysis once data collection is complete.

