3.3 Inclusion of Women and Minorities

Women of all races and ethnicities who meet the above-described eligibility criteria are eligible to participate in this study.

We expect approximately 5% of study participants to be Hispanic/Latino (N=5). We plan to enroll at least 10% Black or African American (N=10), 1% American Indian/Alaska Native (N=1), 5% Asian (N=5). Should we not meet or exceed these estimates, the PI will engage the Cancer Center Health Equity Advisory Group to discuss strategies to enhance recruitment in these target populations.

**THE USE OF LIPOSOMAL BUPIVACAINE FOR PAIN CONTROL FOLLOWING
MASTECTOMY AND IMMEDIATE IMPLANT BASED BREAST RECONSTRUCTION**

Wake Forest Baptist Comprehensive Cancer Center
CCCWU # 99517

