10.2 Analysis of Secondary Objective

10.2.1 For the area under the curve of pain scores at 48 hours, prior studies have found that the area under the curve for pain scores at 72 hours for liposomal bupivacaine infiltration is $441 +/- 182$ and for bupivacaine infiltration is $461 +/- 181^{20}$. A sample size of 40 in each group will have 80% power to detect a difference in means of approximately 25% (115 units) between a Bupivacaine mean, m_1 , of 461 and a Liposomal Bupivacaine mean, m_2 , of 346 assuming that the common standard deviation is 181 using a two group t-test with a 0.05 two-sided significance level. Our study will be powered to detect this difference; we will use an independent t-test to assess statistical significance.

10.2.2 For postoperative narcotic use, prior studies have found the average use of morphine equivalents at 48 hours after mastectomy and tissue expander placement is 3.3¹⁷. This study will also have the ability to detect an effect size of 0.6 between groups, with 45 per group, a two-sided alpha of 0.05, and 80% power. We would expect the patients treated with liposomal bupivacaine to be have a lower average use. We will use an independent t-test to test for differences between groups; if the data are not normally distributed, a log transformation will be used prior to using the t-test.

10.2.3 For length of stay, the reported LOS has been shown to be 41-47 hours on average²¹. We believe Exparel will shorten this time; the study will have the ability to detect an effect size of 0.60 between the 2 groups. We will use an independent t-test to test for differences between groups; if the data are not normally distributed, a log transformation will be used prior to using the t-test.

10.2.4 For readmission rates, patients who underwent tissue expander breast reconstruction have a readmission rate of approximately 4.34%²². We anticipate a readmission rate of approximately 2%. Our study is not powered to detect differences in the 2 arms in this parameter.

10.2.5 For opioid related adverse effects, we predict a 50% incidence of opioid related adverse events in our study. With 45 per group, our study is not powered to detect differences between the 2 arms unless the difference is much larger than anticipated. With a 60%

THE USE OF LIPOSOMAL BUPIVACAINE FOR PAIN CONTROL FOLLOWING
MASTECTOMY AND IMMEDIATE IMPLANT BASED BREAST RECONSTRUCTION

Wake Forest Baptist Comprehensive Cancer Center
CCCWU # 99517

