10.3 Power and Sample Size

We will have a power of 80%, as described in 10.1.1, with a sample size of 25 patients in each arm for a total of 50 patients

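### At 25 per arm the primary comparison has about 50–55% power for the stated effect sizes of 0.6 and 0.57, not 80%; the effect detectable with 80% power is about 0.81–0.86 SD

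*Combined protocol and SAP*

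**What the plan says.** Section 10.1.1 (Analysis of Primary Objective) allows for 10% attrition and names an independent t-test "with a 2-sided alpha of 0.05 and power of 80"%. The effect is standardised as the difference in means over the standard deviation of the 48-hour pain score ("Assuming a similar standard deviation in pain score at 48 hours" in both arms). The claimed detectable effect is one "of 0.6 between the 2 groups with 25 subjects per arm. We will recruit 25 subjects per arm; if there is no attrition"; for that last case the section puts the figure at 0.57.

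Section 10.3 (Power and Sample Size) rests on this: "We will have a power of 80%, as described in 10.1.1, with a sample size of 25 patients in each arm", 50 patients in total. Section 10.4 also gives a goal of 50.

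Other parts of the document use different sizes:

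- Section 10.2.2 (narcotic use): "This study will also have the ability to detect an effect size of 0.6 between groups, with 45 per group", with the same alpha and power.
- Section 10.2.3 (length of stay) repeats an effect size of 0.60.
- Section 10.2.1 (area under the curve) is calculated with 40 per group.
- Section 10.2.5 (opioid adverse effects) is calculated with 45 per group.
- Section 3.3 (Inclusion of Women and Minorities): "We plan to enroll at least 10% Black or African American (N=10"), and 5% is equated with 5 patients. Both imply a total of about 100.

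**The concern.** The same effect size, alpha and power are attached to 25 per arm in 10.1.1 and to 45 per arm in 10.2.2, and both cannot be right. As a rule of thumb, 80% power for an effect of 0.6 SD needs more than 40 per arm, so the figure in 10.1.1 looked wrong on sight.

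Sections 10.1.1 and 10.3 are the only justification given for the trial's size on its primary outcome. If the figure is wrong, those approving or joining the trial are told that it has a four-in-five chance of finding a 0.6 SD benefit when the chance is close to one in two. A non-significant result could then be taken as fair evidence against a benefit of that size when it is not.

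**Working it through.** **Inputs, all from 10.1.1 and 10.3:** two parallel arms, 1:1; independent t-test; two-sided alpha 0.05; power 80%; effect size d = 0.6 (with attrition) or 0.57 (without); 25 per arm; attrition 10%. No standard deviation is needed because the effect is standardised.

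**Step 1. Sample size the stated effects require.** By the normal approximation, n per arm = 2(1.960 + 0.842)² / d².

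- d = 0.6: 2 × 7.85 / 0.36 = 43.6, so 44. The exact t-test calculation gives 44.6, so 45.
- d = 0.57: 2 × 7.85 / 0.3249 = 48.3, so 49. The exact t-test calculation gives 49.3, so 50.

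**Step 2. Reproduce the plan's figures.** They come out at 45 and 50 per arm. The 80% detectable effect is 0.597 at 45 and 0.566 at 50, which round to 0.60 and 0.57. Also 45 / (1 − 0.10) = 50, so the pair fits 45 evaluable out of 50 recruited per arm, 100 in total.

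**Step 3. Power at the planned size.** The noncentrality parameter is d√(n/2), referred to a noncentral t with 2n − 2 degrees of freedom. For d = 0.6 and n = 25 it is 0.6 × √12.5 = 2.12, only just above the critical value of about 2.01, so power must be a little over one half. For d = 0.57 it is 2.02, almost exactly at the critical value.

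| n per arm | Power, d = 0.6 | Power, d = 0.57 | Effect detectable with 80% power |
|---|---|---|---|
| 22 | 49.4% | 45.5% | 0.865 |
| 22.5 (25 less 10%) | 50.3% | 46.4% | 0.855 |
| 23 | 51.2% | 47.2% | 0.845 |
| 25 | 54.7% | 50.6% | 0.809 |
| 45 | 80.4% | 76.2% | 0.597 |
| 50 | 84.4% | 80.6% | 0.566 |

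The normal approximation at 25 per arm agrees: 56.4% for 0.6 and 52.2% for 0.57.

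**Step 4. Other readings.** One-sided alpha 0.05 at 25 per arm gives 67% for 0.6 and 63% for 0.57, with a detectable effect of 0.71; the text says two-sided in any case. A paired t-test on 25 pairs has a detectable effect of 0.584, but it does not fit two parallel arms. No reading gives 80% for the stated effects at 25 per arm.

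**Step 5. Size in pain-score points.** The documents give no standard deviation for the pain score. With an assumed SD of 1.5 to 2.5 points, 0.6 SD is 0.9–1.5 points. The difference actually detectable with 80% power is 0.809 × SD = 1.2–2.0 points at 25 per arm, or 0.865 × SD = 1.3–2.2 points at 22.

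**Step 6. Secondary statements at 25 per arm.**

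- Section 10.2.1: 115 / 181 = 0.635 SD gives 80% power at 40 per group, as stated, but about 60% at 25 and 54% at 22.
- Sections 10.2.2 and 10.2.3: the effect of 0.6 has the same 54.7% power as the primary analysis.
- Section 10.2.5: 60% against 29% (a 31-point difference) by Fisher's exact test has about 54% power.

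**The case against.** The arithmetic cannot be disputed, but four objections deserve an answer.

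**The paragraph need not contradict itself.** If 25 means recruited in both sentences, one figure allows for losses and the other does not. That reading is coherent. Even the ratio fits: 0.6 / 0.57 = 1.05 and √(1/0.9) = 1.05. Only if the first 25 is taken as the evaluable number does one n do two jobs. Either way the effect sizes are wrong for 25.

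**How the error arose is an inference.** No text records a reduction from 50 to 25 per arm. The fit to 45 and 50, the 45 per group in 10.2.2 and the counts in 3.3 support that explanation, but the error does not depend on it.

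**The primary outcome may be less variable than the 48-hour score.** Sections 2.1.1 and 5.1.1 define it as the mean of 12-hourly scores over 48 hours. With four scores of equal SD, a constant difference of 0.6 of that SD and within-patient correlation ρ, the variance falls by the factor (1 + 3ρ)/4. Power at 25 per arm would then be about 80% at ρ = 0.4, 75% at 0.5, 66% at 0.7 and 62% at 0.8. This has force, but the documents give no correlation, and 10.1.1 bases both the calculation and the test on the single 48-hour score. It does not rescue the statement as written.

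**Keeping 25 per arm leaves open whether 0.81–0.86 SD is plausible.** This stands. The one comparison with plain bupivacaine that the document cites, in 10.2.1 (441 against 461, SD 181), is 20 / 181 = 0.11 SD, in a different operation and over 72 hours. The plan should justify whatever effect it names.

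**Conclusion.** The power statement is wrong as written and must be corrected. For the analysis that 10.1.1 describes, 25 per arm gives 54.7% power for 0.6 and 50.6% for 0.57. With 22 evaluable per arm after attrition, power for 0.6 is 49.4%. The effect detectable with 80% power is 0.81 SD without attrition and about 0.86 SD with it, roughly 35–44% larger than the 0.6 claimed (0.809 / 0.6 = 1.35; 0.865 / 0.6 = 1.44). The type II error for 0.6 is 45–51%, against a stated 20%.

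This rests only on the plan's own alpha, sidedness, test, allocation and attrition rate. The figures in pain-score points rest in addition on the assumed SD of 1.5–2.5.

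**What to change.** Keep 25 per arm and change the text as follows.

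1. **10.1.1 and 10.3:** state that, with 25 recruited per arm, the trial has 80% power for an effect size of 0.81, or 0.86 with about 22 evaluable after 10% attrition; and that power for 0.6 is about 55%, or 49% after attrition. Delete the 0.57 sentence. Say why an effect of 0.81–0.86 SD is a reasonable target, or say plainly that the size was set by feasibility.
2. **10.2.2 and 10.2.3:** replace the effect size of 0.6, and the 45 per group in 10.2.2, with the same corrected figures.
3. **10.2.1 and 10.2.5:** restate for 25 per arm (about 60% and 54% power for the differences quoted there), and withdraw the claim in 10.2.1 that the study is powered for its difference.
4. **3.3:** recompute the counts for 50 patients. For example, 10% is 5, and 5% is 2.5, that is 2 or 3.
5. **Reporting:** commit to giving the treatment difference with its 95% confidence interval, so that a non-significant result is not read as no effect.

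The cost is an amendment to wording, with no extra patients and no change in conduct; the stated sensitivity becomes less favourable. If the sponsor would rather keep 80% power for 0.6, that requires 45 evaluable and 50 recruited per arm, 100 in total. At the 25 patients a year in 10.4 that is 100 / 25 = 4 years of accrual, not 2.

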2.0 Objectives

2.1 Primary Objective(s)

- 2.1.1 The primary objective of this clinical study is to evaluate the effect of Exparel on mean postoperative pain levels in patients who have undergone mastectomy and breast reconstruction within the first 48 hours. We hypothesize that Exparel will decrease mean postoperative pain levels within the first 48 hours.

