5.0 Study Outcomes and Study Measures

5.1 Primary Outcome

5.1.1 The primary outcome of this study is the mean visual analog scores (scale of 0-10) within the first 48 hours postoperatively. This will be measured every 12 hours for the first 48 hours and will be assessed by the level of breast pain associated with arm movements while eating.

5.1.1.1 Visual analog scores in mastectomy patients with oral and IV narcotics are approximately 5.0 at 24 hours and 4.8 at 48 hours¹⁷

5.1.1.2 For patients with local infiltration of Liposomal bupivacaine after implant based reconstruction, visual analog scores at 24hrs were 3.8 on average¹⁸

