The study will be double blinded to both patients and providers including plastic and general surgeons involved in their operative care. We will enroll our patients in pharmacy randomization program, in which the pharmacy will deliver the appropriate medication per assigned group.

To monitor our primary outcomes, patients will be asked to rate their pain level on a visual analog scale (Table 2, Appendix Z) with activity every 12-hours after surgery during their post-procedure stay. The activity for which they will rate their pain will be the arm movements associated with eating. In the hospital, their visual analog scores will be provided to each patient in person by their nurse every 12 hours. Subject's pain scores will continue to be recorded every 12 hours via a phone call from a study team member for the first 48 hours after discharge. Additionally, while in the hospital, the amount of narcotics used will be recorded and converted into morphine equivalents.

Upon discharge, patients will be given a sheet to record their pain level and the amount of narcotics & benzodiazepines used (Appendix K). Both the amount of narcotics & benzodiazepines and the pain level are to be reported at the time of taking any narcotics & benzodiazepines. Patients will follow up with our clinic at 1 week, 3 weeks, and 5 weeks postoperatively. At week 1 patients will bring in their medication and pain diary, and fill out a pain assessment (Appendix G) in addition to a questionnaire assessing breast cancer surgery

THE USE OF LIPOSOMAL BUPIVACAINE FOR PAIN CONTROL FOLLOWING MASTECTOMY AND IMMEDIATE IMPLANT BASED BREAST RECONSTRUCTION

Wake Forest Baptist Comprehensive Cancer Center
CCCWU # 99517

disability (Appendix H)²³. During subsequent appointments made at 3 and 5 weeks postoperatively, they will be assessed and receive the pain assessment and breast cancer surgery disability assessments as well. When tissue expansion is initiated will be determined by the primary surgeon, but we will track the dates of the initiation of expansion as this will impact pain scores within the electronic medical record.

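### The primary outcome is mean pain over the first 48 hours in Sections 2 and 5, but Section 10.1.1 names, powers and tests only the single score at 48 hours

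*Combined protocol and SAP*

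**What the plan says.** Section 2.1.1 states the hypothesis: "We hypothesize that Exparel will decrease mean postoperative pain levels within the first 48 hours". Section 5.1.1 defines the outcome to match: "The primary outcome of this study is the mean visual analog scores (scale of 0-10) within the first 48 hours postoperatively". It adds the schedule, "This will be measured every 12 hours for the first 48 hours", which gives four readings if they fall at 12, 24, 36 and 48 hours.

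Section 10.1.1 is headed as the analysis of the primary objective, but says "The primary outcome will be the pain score observed at 48 hours". Its power statement begins "Assuming a similar standard deviation in pain score at 48 hours", and the independent t-test at 0.05 is applied to those scores. The section ends: "Two-sided ANOVA will be performed for statistical analysis once data collection is complete". No outcome, factor or time point is given for that ANOVA.

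The only analysis in Section 10 that covers the whole 48 hours is the area under the curve in 10.2.1, listed under the secondary objectives.

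**The concern.** An average over an interval and one reading at its end are different variables, with different standard deviations and possibly different treatment effects. A benefit confined to the first 24 to 36 hours would lower the mean and could be invisible at hour 48. A late benefit would do the reverse. If 10.1.1 is followed, the primary p-value answers whether pain differs at hour 48 and leaves the hypothesis of 2.1.1 without a primary test.

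The protocol gives no order of precedence. If the two results differ, the deciding one could be chosen after the data are seen. Section 10.6 plans an interim look at the primary outcome once each group has at least 10 patients, so the choice should be fixed before then.

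**Working it through.** **Side by side**

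| Place | Primary variable |
|---|---|
| 2.1.1 | mean pain level within the first 48 h |
| 5.1.1 | mean VAS within the first 48 h, read every 12 h |
| 10.1.1, outcome sentence | score observed at 48 h |
| 10.1.1, power | SD of the score at 48 h |
| 10.1.1, t-test | those same scores |
| 10.1.1, ANOVA | not stated |
| 10.2.1 | AUC over 48 h, secondary |

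The contradiction follows from this text alone. The arithmetic below only shows how far the two tests could diverge.

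**The plan's own power figure.** Section 10.1.1 claims 80% power, two-sided 0.05, for an effect of 0.6 SD with 25 per arm (0.57 without attrition). It does not reproduce. By the noncentral t, 0.6 needs 45 per arm and 0.57 needs 50. At 25 per arm the power for 0.6 is 55%, and the effect detectable with 80% power is 0.81 SD (0.86 with 22 per arm left after 10% attrition). The pair 0.6 and 0.57 fits 45 evaluable out of 50 recruited per arm (45/0.9 = 50). This is a separate sample-size error and adds no weight to the present point.

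**Illustration: assumptions.** 25 per arm (Section 10.3), four readings, equal SD at each, equal correlation ρ between readings. Neither ρ nor the effect profile is in the documents. I take ρ = 0.5, with 0.3 to 0.7 as the range, and three profiles in units of the single-reading SD:
- constant: 0.6 at every reading
- fading: 0.9, 0.7, 0.5, 0.3 (average 0.6)
- growing: 0, 0.3, 0.6, 0.9 (average 0.45)

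**Formulas.** Variance of the mean relative to one reading = (1 + 3ρ)/4, which is 0.475, 0.625 and 0.775 for ρ = 0.3, 0.5 and 0.7. Standardised effect of the mean = average effect / √ratio. For ρ = 0.5 this is 0.6/√0.625 = 0.76 for the constant and fading profiles, and 0.45/√0.625 = 0.57 for the growing one. For the 48-hour score the standardised effects are 0.6, 0.3 and 0.9. Power is from the two-sided noncentral t. Disagreement (one test significant at 0.05, the other not) is from 100,000 simulated trials per setting.

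| Profile | Power, 48 h score | Power, mean: ρ = 0.5 (0.3 to 0.7) | Disagreement: ρ = 0.5 (0.3 to 0.7) |
|---|---|---|---|
| constant | 55% | 75% (85 to 66%) | 26% (34 to 18%) |
| fading | 18% | 75% (85 to 66%) | 57% (68 to 48%) |
| growing | 88% | 50% (62 to 43%) | 38% (29 to 45%) |

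**Sensitivity.** If correlation decays with lag (0.5 per 12-hour step), the variance ratio is 0.516 and disagreement is 33%, 65% and 33%. Both tests being significant in opposite directions occurs in at most 0.05% of trials in any scenario run.

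**Reading clock (a lesser point).** Section 5.1.1 counts from surgery. The Section 6.0 calendar marks 12-hourly scores only after discharge. Section 6.1 has readings every 12 hours after surgery while in hospital, then says they "will continue to be recorded every 12 hours via a phone call from a study team member for the first 48 hours after discharge", which can mean that the clock carries on or restarts. If it restarts, discharge at 36 h (the stay 5.2.3.2 expects with liposomal bupivacaine) still gives a 48 h reading, since 36 + 12 = 48. Discharge at 41 to 47 h (the average cited in 5.2.3.1) gives 12, 24 and 36 h and then 41 + 12 = 53 h to 47 + 12 = 59 h, with nothing at 48 h.

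**The case against.** The best defence is that the protocol writes loosely about time. Section 10.2.1 says "For the area under the curve of pain scores at 48 hours", and an area under the curve cannot be a single reading, so the score at 48 hours in 10.1.1 may also have been meant as the whole period. That lowers certainty about intent. It does not rescue the text: 10.1.1 speaks of one score observed at one time, 5.1.1.1 quotes separate values for 24 hours (5.0) and 48 hours (4.8), and the wording would need correcting on either reading.

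Second, the percentages rest on assumed inputs, and the constant-effect figure partly reflects low power. With 45 per arm it falls to about 15%, and with ρ = 0.9 at 25 per arm to about 9%. That is fair. The other profiles are less sensitive: at ρ = 0.9 and 25 per arm, fading gives about 40% and growing about 51%. They remain chosen profiles, not predicted ones.

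Third, the contradiction could equally be removed by changing Sections 2 and 5 to the 48-hour score. Section 1.0 describes a local effect lasting up to 72-96 hours for the liposomal form and cites a meta-analysis in which infiltration with bupivacaine or ropivacaine lowered pain only at 2 hours, so a late endpoint could be deliberate. This stands as an option for the sponsor. The objective, hypothesis and outcome definition all point to the mean, however, and only 10.1.1 departs from them.

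**Conclusion.** The concern holds and must be fixed. As written, the primary test addresses a different variable from the one in the primary hypothesis, and no other passage repairs this. That conclusion rests on the text and needs no assumption.

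The size is illustrative. With 25 per arm and between-reading correlation of 0.3 to 0.7, the two candidate tests split on significance in roughly 18 to 68% of trials, depending on correlation and on how the effect changes over time. Neither variable is always the more powerful: the mean does better under a constant or fading effect, the 48-hour score under a growing one. The reading clock, the undefined ANOVA and the sample-size error are side matters, and the verdict does not depend on them.

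**What to change.** Align 10.1.1 with Sections 2 and 5. Suggested wording: *The primary outcome is each patient's mean of the 12-hourly VAS readings over the first 48 hours after surgery (12, 24, 36 and 48 h), compared between arms by a two-sided independent t-test at 0.05.*

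Then:
- Make the 48-hour score a secondary outcome.
- State the outcome, factors and time points for the ANOVA, or delete it.
- Restate power for the mean score. As a standardised effect of the mean, 25 per arm detects about 0.81 SD with 80% power (0.86 with 22 per arm).
- Give a rule for missing readings. Using the mean of the available readings when one is missing costs little precision (at ρ = 0.5 the variance ratio is (1 + 2 × 0.5)/3 = 0.667 against 0.625). It can bias the comparison if the gaps cluster at one time or in one arm, so add a sensitivity analysis and a rule for more than one missing reading.
- Say what event starts the clock. Show the surgery-timed readings in the Section 6.0 calendar and make clear in 6.1 that they continue to 48 hours after surgery wherever the patient is. Keep the post-discharge calls, which can also serve the trajectory analysis in 10.2.6.

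Cost: wording, a calendar addition and a redone power statement. If calls are now timed from discharge, a patient who leaves before 48 h and off the 12-hour grid needs one or more extra calls (one, at 48 h, for discharge at 41 to 47 h). There are two drawbacks. The mean nearly duplicates the secondary AUC (correlation 0.98 to 0.99 under the equal-correlation assumption), and primary power falls from 88% to 50% in the growing-effect scenario. If the sponsor prefers the 48-hour score for that reason, Sections 2.1.1 and 5.1.1 must be changed instead, before any unblinded data are examined.
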